**Brief Intervention for Justice-Involved Substance Users:
Harnessing Mechanisms of Change**

NCT03308877

04/01/2017

D.7. Data Analysis. A baseline check of randomness will be conducted for each variable collected. Categorical variables will be analyzed using chi-square tests; continuous variables with ANOVAs. To assess Hypothesis 1 continuous outcomes, Analysis of Covariance will be used. The effects of BMI+SC on commitment to change, self-regulation, and substance use will be assessed immediately following intervention. Longer term substance use effects will be examined at 6-month follow-up. For substance use toxicology results, logistic regression will be used. In all instances, alpha = .05; covariates will include gender, race, age, and the outcome baseline score of interest as well as any other variables found to differ at baseline. Additionally, effect sizes will be examined using marginal means.⁷¹ Structural equation modeling (SEM) will be used to test the hypothesis that the effect of BMI+SC on substance use will be mediated by increases in commitment to change and self-regulation (Figure 2).⁷² *Substance use status* at six month follow-up is the key outcome of interest. We hypothesize that effects on six month substance use are mediated, in part, by BMI+SC effects on commitment to change and self-regulation. Substance use status will be measured using two indicators, percent days abstinent and the urine screen result. *Commitment to Change* will be measured using two indicators at each time point, the Readiness Ruler and the CLEAR change talk score at both baseline and immediate post. Two indicators will also be used to assess *Self-Regulation* at baseline and immediate post: Self-Regulation Questionnaire scores and Balloon Analog Risk Task scores. Additionally, demographic variables will be statistically controlled for in the model (gender, age, race, ethnicity). The MPLUS statistical package⁷³ will be used for SEMs. To provide a metric for each latent construct and to identify the model, the first construct loading for each latent variable will be set at 1.0. A two-step approach examining the model will be undertaken.⁷⁴ First, using confirmatory factor analytic techniques, a test of the proposed measurement model will be conducted and any needed modifications to this model, including testing for measurement invariance over time, will be undertaken prior to examining model fit. The second step involves an examination of the structural portion of the model. The model suggests that BMI effects on substance use are not only direct, but also indirect, mediated by effects on commitment to change and self-regulation. Baseline substance use status, commitment to change, and self-regulation will be controlled for, aiding precision in detecting treatment effects. Fit of the model will be assessed using a chi-square statistic, as well as the more approximate fit indices of the root mean square error of approximation (RMSEA),⁷⁵ the comparative fit index (CFI),⁷⁶ and the standardized root mean square residual (SRMR). Using various cutoffs for fit assessment helps to minimize Type I and Type II errors.⁷⁷ Recommendations that adequate fitting models have $CFI > .95$, $RMSEA < .06$, and $SRMR < .08$ will be adopted here. BMI indirect effects on 6 month substance use will be tested using the bias-corrected confidence limits.⁷⁸ Significance will be assessed by whether or not the 95% confidence limits contain zero. The bias corrected approach has been shown to provide the most accurate confidence limits and greatest statistical power when compared with other existing approaches for detecting mediation.⁷⁸ Multi-group structural equation modeling will be used to test moderated mediation. Two groups (high vs. low/moderate on affective psychopathy) will be compared. We will isolate differences across models by first examining if measurement parameters are equal across groups. Model differences across groups will be tested using the chi-square difference test. Next, we will test for structural differences across groups, examining regression parameter estimates for equality, followed by an examination of latent variables' variances and means across the groups. Such moderated-mediation will allow for isolation of BMI effects on latent variable means, controlling for process differences across the groups. Four exploratory analyses will also be conducted. The first will examine longitudinal change in substance abuse using growth curve analyses. Substance use is measured at baseline, 4 times during the intervention period, and at 6-month follow-up (6 time points). Time will be modeled so that the intercept reflects baseline status and subsequent time points will be modeled as weeks from baseline. Both linear and curvilinear (quadratic) change

will be examined using the same covariates as previously mentioned. Here, we are interested in the time by condition interaction term, addressing whether the trajectory of substance use differs across the BMI+SC and SC groups. Second, we will determine whether BMI+SC had an effect on violent recidivism using logistic regression. We will also use the structural equation models above to examine mediational and moderated mediation effects of BMI on violent recidivism. Finally, we will also examine the moderated mediation models across gender and race (white vs. black) to determine if mean and/or process differences exist for males and females as well as for White and Black participants. (Numbers of other races/ethnicities are likely to be too low for separate analysis).

D.7.1 Power, Missing Data, and Type 1 Error Protection. For analyses involving continuous mean differences Optimal Design software was used to assess statistical power. With a sample size of 416, we are adequately powered ($> .80$) to detect a small standardized effect with baseline covariates explaining 40% of the outcome variance (n required = 265 to achieve .80 power). Should baseline covariates explain only 30% of the variance, we are powered at .78 to detect small effects. The inclusion of baseline covariates typically improves precision (at the cost of degrees of freedom)⁷⁹ For the logistic analyses predicting urine screen substance use results and 12-month recidivism, power analyses were conducted using the Stata statistical software program. We are interested in the power of treatment status to significantly detect a difference in positive urine screens and violent recidivism by 12 months. In a likely scenario of 50% positive urine screens, we are adequately powered (.80) to detect a 14% or more difference in rates. Power improves slightly as the baseline rates drift away from 50%. Typical 12-month violent recidivism rates are 20%. Here, we are adequately powered to detect a 12% point difference in rates, even if average absolute baseline covariate correlation with treatment is .3. For the structural equation model to be tested,⁸⁰ our approach allows for the testing of a null hypothesis of not good fit, reversing the role of the null hypothesis in conventional tests of model fit, so that a significant result provides strong support for good fit. With an expected sample size of 416, adequate power ($> .95$) to reject an hypothesis of close fit ($RMSEA > .08$) with 94 degrees of freedom (df) given a population $RMSEA$ of .05 was obtained (proposed model including age, gender, 2 race variable = 94 df). Additionally, adequate power (.99) to reject a hypothesis of not-close fit was obtained. Here, if model fit is extremely good ($RMSEA < .01$), and we test the hypothesis that fit is not close, we have greater than .95 power to reject the null hypothesis that $RMSEA > .05$. Even if sample size drops to 300, power for both the hypothesis of close fit and the hypothesis of not close fit remains above .90. As more degrees of freedom are introduced with the addition of multi-group modeling (psychopathy, gender, race), power improves on the above estimates. For analyses examining mean and rate differences, pairwise deletion of missing data will be used, thus retaining all available information. As a form of sensitivity analysis, however, multiple imputation of missing data will be conducted, which has consistently demonstrated less biased parameter estimates than most other approaches to the handling of missing data.⁸¹ To help control for Type 1 error, the Benjamini-Hochberg (BH) method⁸² will be used to adjust for the multiple comparisons proposed. The BH method adjusts for multiple comparisons by controlling the false discovery rate instead of family-wise error rate. It is less conservative than the more traditional Bonferroni methods, yet still provides adequate protection against Type 1 error.

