**Brief Intervention for Justice-Involved Substance Users:
Harnessing Mechanisms of Change**

NCT03308877

04/01/2017

Study Design

D.3. Overview. We propose a rigorous RCT using a matched-pairs design to test *a priori* hypotheses based on the findings of Preliminary Study 2, while investigating the mechanisms by which people change. In line with renewed national efforts to promote reproducible science, this study is, among other things, an attempt to replicate the primary findings of our published work in a larger sample. We incorporate appropriate blinding, and validated, multi-method measurement of constructs. We will compare the efficacy of BMI+SC versus SC across two groups: a) individuals with low/moderate affective psychopathy (affective score < 5) and, b) individuals with high affective psychopathy (affective score > 5). In Session One, individuals who are within their first three weeks at MCPS will be recruited and briefly screened for substance use. Individuals who report substance use once per week or more and meet the Drug Abuse Screening Test cutoff score of 3 or higher⁵¹ will continue in the study. Session Two (Baseline Assessment A) will involve a brief assessment of general psychopathology and detailed assessment of psychopathy and frequency of use of a range of substances. Baseline assessment B will include assessment of putative mediators (self-regulation and commitment to change), along with an assessment of treatment services use over the past 6 months. After Baseline Assessment B, participants will be randomized (coin toss) to either BMI+SC or SC in pairs that are matched according to affective psychopathy level. That is, two individuals with low/moderate affective psychopathy will be randomized (one each) to either BMI+SC or SC. The same will occur with individuals who are high in affective psychopathy. The next session will occur as close to baseline as possible, followed by sessions at 2, 4, and 6 weeks post-baseline. These meetings will involve assessments of frequency and type of substance use (both groups), and the delivery of our BMI (treatment group only). The outcome variables will be 1) frequency of substance use (proximal; percent days abstinent at 6 months) and 2) violent criminal recidivism (distal; charges at 12 months).

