D.3.1. Sample. A total of 536 participants will be recruited and randomized to either the BMI+SC or SC condition during the first four and a half years of the study. The proposed sample size is feasible based preliminary data (i.e., approximately one eligible participant per recruiting day). We will screen approximately 545 participants per year (in 1:1 format). Based on preliminary data, 22% of these participants ($n=119$) will meet eligibility criteria for the study. We estimate attrition during follow-up at approximately 25% based upon Preliminary Study 2, leaving approximately 91 participants per year (or a total of 416 across 4.5 years) for analysis.

D.3.2. Rationale for standard care control group. Ultimately it is important to determine whether the BMI is efficacious relative to a specific active comparison condition. However, it is first necessary to determine whether the BMI+SC works at all compared to SC, taking into account affective psychopathy scores. Approximately 50% of all MCPS clients are mandated through the court system to complete substance abuse treatment, though the number who do so is lower. For the proposed study, the SC condition will include individuals who receive levels of non-study intervention that vary widely, from none to substantial. This real world condition provides the potential for useful generalization of results to other supervision programs, and is an appropriate comparison for assessing a brief intervention that may best serve as an adjunct to SC. The SC condition will consist of no research-related intervention beyond the baseline assessment session, but we will measure and analyze all non-study treatment participation carefully. Individuals in MCPS do not receive substance use services onsite, though some are referred to community providers for treatment. For anyone involved in non-study treatment, we will measure number of sessions and type of treatment in order to ensure that comparisons between BMI+SC and SC take into account all extra-study treatment.

D.4. Overview of Study Appointments

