change and self-regulation as mechanisms of change. Commitment to change. 1) We will code change talk that occurs in BMI sessions using the Client Language Easy Rating (CLEAR) coding sheet.⁶⁹ Audiotaped sessions will be transcribed and coded for the proportion of participant change talk: change talk/(change talk+sustain talk+neutral), yielding the percentage of speech utterances that are change talk. 2) The readiness ruler, an efficient and reliable measure of motivation to change⁵⁹, will be used at baseline and following each intervention session for an assessment of readiness to change. Self-Regulation. The Self-Regulation Questionnaire⁵⁸ will be administered during the screening session and after each intervention session to assess increases in self-regulation that have occurred. The BART,⁶⁰ a computerized behavioral task, will provide a second method of assessing self-regulation and will be administered after the last intervention session.

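### The ANCOVA and logistic models name neither affective psychopathy group nor a treatment-by-group term, although the trial randomises within that group and frames its comparison across it

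*SAP*

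**What the plan says.** Protocol D.3 sets the aim: "We will compare the efficacy of BMI+SC versus SC across two groups", the groups being low/moderate and high affective psychopathy. Participants are "randomized (coin toss) to either BMI+SC or SC in pairs that are matched according to affective psychopathy level", and D.4.3 repeats this. D.3.2 explains the choice of control: "it is first necessary to determine whether the BMI+SC works at all compared to SC, taking into account affective psychopathy scores".

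SAP D.7 uses ANCOVA for the continuous outcomes of Hypothesis 1 and logistic regression for toxicology. For these models "covariates will include gender, race, age, and the outcome baseline score of interest as well as any other variables found to differ at baseline". The exploratory growth curves reuse those covariates and add only time by condition. The exploratory logistic model for violent recidivism states only an overall BMI+SC effect.

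Affective psychopathy enters the SAP through the multi-group SEM: "Two groups (high vs. low/moderate on affective psychopathy) will be compared". After the measurement parameters, the structural part is tested by "examining regression parameter estimates for equality". The SEM is also extended to mediation and moderated mediation for violent recidivism.

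D.7.1 gives power for overall mean differences, overall differences in rates, and SEM model fit.

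**The concern.** The factor that defines the randomisation and the scientific question is absent from the stated form of the models that estimate efficacy directly.

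The allowance for variables that differ at baseline does not close the gap. Matching balances the group between arms, so a baseline test would rarely flag it, and that route never supplies an interaction. It also selects the remaining covariates by significance test in a randomised trial, where differences arise by chance.

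At stake is interpretation. If the direct models report only an average, a uniform benefit and a benefit confined to one group can look the same. Any by-group contrast added later to those models would be post hoc, in a trial that sets out to replicate earlier findings. The average effect is still a legitimate first question, so the group term supplements it and does not replace it.

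**Working it through.** **The plan's own figures.** There is no stated power for a group difference to reproduce. The main-effect figures in D.7.1 (265 required at R² = .40; power .78 at N = 416 and R² = .30) do not reproduce with a two-sided test at d = 0.20, which gives 472 and .68. Nor are they compatible with each other: 265 at R² = .40 implies 265 × .70/.60 ≈ 309 at R² = .30, fewer than 416, so power there would exceed .80. That is a separate matter, and nothing below depends on it.

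**Inputs.** N = 402, from 536 randomised and 25% attrition (Protocol D.3.1: 536 × .75); the SAP's 416 is also tried. R² = .40 (D.7.1). Alpha .05, taken as two-sided. The share in the high group, f, is not given, so 50%, 30% and 20% are shown. Allocation is 1:1 within group. The scenario, d = 0.30 in low/moderate and 0 in high, is assumed.

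**What one average hides.** With f = .30 the pooled effect is .70 × 0.30 + .30 × 0 = 0.21 SD, the same as a uniform 0.21 SD.

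**Standard errors.** Average effect: √(4(1−R²)/N) = √(2.4/402) = 0.0773. Difference in effect between groups: √(4(1−R²)/(Nf) + 4(1−R²)/(N(1−f))). At f = .50 this is √(2.4/201 + 2.4/201) = 0.1545; at .30, √(2.4/120.6 + 2.4/281.4) = 0.1686; at .20, √(2.4/80.4 + 2.4/321.6) = 0.1932. Power is from the noncentral t, for which 80% power needs about 2.81 standard errors. Interval half-widths are 1.96 × √(4(1−R²)/n in the group).

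| | f = .50 | f = .30 | f = .20 |
|---|---|---|---|
| Pooled effect (SD) | 0.15 | 0.21 | 0.24 |
| Power, pooled test | .49 | .77 | .87 |
| Power, interaction (0.30 SD) | .49 | .43 | .34 |
| Detectable group difference (SD) | 0.43 | 0.47 | 0.54 |
| 95% CI half-width, low/moderate | 0.21 | 0.18 | 0.17 |
| 95% CI half-width, high | 0.21 | 0.28 | 0.34 |

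The detectable average effect is 2.81 × 0.0773 = 0.22 SD.

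**Sensitivity.** At N = 416, interaction power is .50, .44 and .35, and the detectable difference 0.43, 0.47 and 0.53 SD. At N = 402 and R² = .30, power is .43, .38 and .30, and the detectable difference 0.47, 0.51 and 0.59 SD. For a difference of only 0.20 SD (N = 416, R² = .40), power is .26, .23 and .18.

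**Toxicology.** Take the SAP's 14-point difference (50% to 36%) in low/moderate only, with 50% in both arms of the high group. The interaction on the log-odds scale is ln[(.50/.50)/(.36/.64)] = 0.575. At N = 402 its standard errors are 0.403, 0.438 and 0.501, giving power .30, .26 and .21.

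**Omitting the group as a main effect.** If it explains a share r of residual variance, the true alpha is 2(1 − Φ(1.96/√(1−r))): .044 at r = .05 and .039 at r = .10. At d = 0.20 and N = 402, power is .740 against .757 with the group included, and .746 against .779. The tests become slightly conservative.

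**Baseline testing.** At .05, chance alone flags about .05 × 20 = 1 to .05 × 40 = 2 variables if 20 to 40 are tested (count assumed).

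**The case against.** The strongest reply is that moderation is already pre-specified on the key outcome. The multi-group SEM tests regression paths for equality across the groups. These include the direct BMI path to a substance-use factor whose indicators are percent days abstinent and the urine screen, and freeing the paths gives group-specific estimates. Violent recidivism is covered in the same way. This stands: a moderation analysis is planned.

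It is, however, a less direct answer to the question in Protocol D.3. The direct path is net of the mediators, so its equality is not equality of the total BMI effect. The outcome is a latent composite, and the result depends on a measurement model open to modification. The commitment factor has a Readiness Ruler indicator given to everyone at baseline, but its second indicator is available in one arm only: "We will code change talk that occurs in BMI sessions using the Client Language Easy Rating (CLEAR) coding sheet" (Protocol D.5.2). No BMI effect on percent days abstinent or toxicology in each group is stated.

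A second reply is that the wording of Hypothesis 1 is not in the supplied text, and that a covariate list need not name design factors. That is fair, and it limits the finding to what D.7 states.

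A third is that the interaction is weakly powered, more so at 0.20 SD. This is correct. The term is needed to answer the question, not to gain power, and the group-specific intervals will be its most useful output.

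**Conclusion.** The concern holds and should be fixed. D.7 states neither the randomisation factor nor a treatment-by-group term for the ANCOVA and logistic models, and D.7.1 gives no power for a difference in effect between the groups. Its remark that power improves with multi-group modelling follows the model-fit calculations and does not apply to this contrast.

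The trial can detect a group difference of about 0.43 to 0.54 SD with 80% power, roughly twice the 0.22 SD detectable for the average effect or more. This assumes N = 402, R² = .40 and 20% to 50% of participants in the high group, a split the documents do not give. Leaving the group out as a main effect is minor: it costs about 2 to 3 points of power, if the group explains 5% to 10% of residual variance, and does not raise the false-positive rate. Confidence is high on what is and is not stated.

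**What to change.** In SAP D.7:

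- For every ANCOVA and logistic model, prespecify gender, race, age, baseline score and affective psychopathy group as covariates, in place of the allowance for variables that differ at baseline.
- Estimate the average effect from the model without the interaction, then add treatment-by-group in a second model, so that the average is not confused with a reference-group coefficient. Report the BMI effect in each group with its 95% confidence interval beside the average.
- State that significance in one group alone will not be read as a difference between groups.

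In D.7.1, give the detectable difference (about 0.43 to 0.54 SD) and the power for 0.30 SD (about .49 to .34), and say that the remark about multi-group modelling concerns overall model fit only.

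As a clarification, confirm the grouping rule in Protocol D.3. As printed, the bands are below 5 and above 5, leaving a score of exactly 5 in neither. This may be a sign lost in text conversion, but every score must fall in exactly one group.

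The cost is wording only, since the group is already measured and used for randomisation. The plan must say openly that the interaction test is modestly powered, and weaker than the pooled test when the high group is small. The added tests also enlarge the Benjamini-Hochberg set.

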D.5.1. Objective measures. Due to the potential for underreporting of substance use, we will obtain breathalyzer and urinalysis drug screen results at each follow-up using Varian Testcup Pro 5, which provides results for THC, methamphetamines, cocaine, benzodiazepines, and morphine. Results will be used to provide an objective measure of substance use to be incorporated in a secondary analysis. For the assessment of recidivism, The New York State Division of Criminal Justice Services (DCJS) maintains a database of criminal charges and convictions across the state. We will contract with DCJS to provide data at 12 months following the intervention or baseline assessment. Additionally, MCPS maintains a database of county-wide charges and convictions. Because each database does not always capture all official charges and convictions, they will be combined for maximum sensitivity (as in Preliminary Study 1). Criminal charges will be used as the primary measure of recidivism. Finally, recent involvement in non-study interventions will be assessed at baseline as a potential confound, and during follow up for descriptive purposes. Based on the results of the primary analyses, this data may also be used in exploratory analyses to determine whether BMI+SC increased substance abuse services utilization. The Coordinated Care Services, Inc. (CCSI) database will provide a novel way to gain objective information about participant treatment contacts—including substance abuse treatment—during the follow-up period. This health surveillance database is maintained by the Monroe County Office of Mental Health and was utilized in Preliminary Study 1. This database is used to track county-wide service contacts, enabling us to obtain services use data even for individuals who are lost to follow up. Moreover, we are able to cross-reference the objective database with our self-report

measure of non-study treatment for increased sensitivity and to check the validity of self-report treatment data.

D.5.2. Assessing Mediators. We will conduct a thorough, multi-method assessment of commitment to

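### Baseline non-study treatment, which the protocol says comparisons will allow for, enters the models only if a balance test happens to flag it, so it will usually be left out and chance decides the covariate set

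*SAP*

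**What the plan says.** **Covariate rule (SAP D.7).** "A baseline check of randomness will be conducted for each variable collected", by chi-square test or ANOVA. The level and the fixed set are then given: "In all instances, alpha = .05; covariates will include gender, race, age, and the outcome baseline score of interest". The same sentence goes on to leave the set open, admitting further covariates by the wording "as well as any other variables found to differ at baseline". The growth curves "will be examined using the same covariates as previously mentioned". The structural equation model (SEM) has its own list: gender, age, race and ethnicity, plus baseline substance use, commitment to change and self-regulation. Neither list names non-study treatment.

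**Non-study treatment (protocol).**
- D.3.2 describes the standard care (SC) condition as including "individuals who receive levels of non-study intervention that vary widely, from none to substantial". It says session counts and treatment type will be measured so that the comparison of arms allows for treatment outside the study.
- D.3 and D.4.3 place the measurement at Baseline B, before randomisation, using the Economic Form-90 and covering the past 6 months.
- D.5.1 says "recent involvement in non-study interventions will be assessed at baseline as a potential confound". Data from follow-up are kept for description and possible exploratory work.
- D.3 and D.4.3 match pairs on affective psychopathy only.

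**The concern.** The protocol singles out one background variable as needing attention, and the SAP leaves its inclusion to a significance test of balance. With proper randomisation any arm difference at baseline is due to chance. The test therefore carries no information on whether the variable predicts outcome, which is what decides whether adjusting for it helps.

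Two things are at stake. The 6-month percent-days-abstinent analysis will usually forgo whatever precision the variable offers. And nobody can write down the final covariate set for the ANCOVA, the logistic models or the growth curves until the baseline data have been tested, in a study that D.3 presents partly as a replication in the service of reproducible science.

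**Working it through.** **Inputs.** N = 416 analysed, 208 per arm, and R² = .40 or .30 for baseline covariates (SAP D.7.1); alpha = .05 (SAP D.7). Assumed, because the documents do not say: the balance tests use .05; a small effect is d = 0.20; prior treatment adds 2%, 5% or 10% to explained variance beyond the other covariates.

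**1. The plan's own power figure.** D.7.1 gives .78 at R² = .30. With residual SD √(1 − .30) = .837 and d = 0.20, power at 208 per arm is .786 one-sided and .684 two-sided. The figure thus reproduces at d = 0.20 only if one-sided; a two-sided test needs d of about 0.224. Two-sided values are used below.

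**2. How often the rule admits the variable.** For one variable the probability of a significant difference under randomisation is .05, so exclusion is 1 − .05 = 95%. In simulation (20,000 trials per scenario, N = 416) it entered in 4.7% to 5.3% of trials. If treatment use is coded as k independent variables, none enters with probability .95^k: 90% (k = 2), 77% (k = 5), 60% (k = 10).

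**3. Chance covariates.** With 25 to 30 variables tested (assumed, independent), expected false flags are 25 × .05 = 1.25 to 30 × .05 = 1.5. The chance of at least one is 1 − .95^25 = .72 to 1 − .95^30 = .79. If the tests correlate at .3 this falls to 61% to 66%; at .5, to 46% to 51%.

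**4. Precision in the ANCOVA.** The standard error is proportional to √(1 − R²). From R² = .40:

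| Extra R² (assumed) | SE ratio | Equivalent N |
|---|---|---|
| .02 | √(.58/.60) = .983 | 416 × .60/.58 = 430 |
| .05 | √(.55/.60) = .957 | 416 × .60/.55 = 454 |
| .10 | √(.50/.60) = .913 | 416 × .60/.50 = 499 |

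**5. What the rule achieves.** Simulated two-sided power, d = 0.20, other covariates at R² = .30:

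| Extra R² | Never adjust | SAP rule | Always adjust |
|---|---|---|---|
| .02 | .683 | .684 | .696 |
| .05 | .681 | .683 | .710 |
| .10 | .679 | .685 | .743 |

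The rule gains almost nothing over ignoring the variable. Always adjusting gains about 1 to 6 points over the rule. By formula from R² = .40, power goes from .750 to .764, .785 or .822, a gain of about 1 to 7 points.

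**6. Type I error under the rule.** Simulated at .050, .049 and .046 for the three cases. The Monte Carlo standard error is √(.05 × .95/20,000) = .0015, so there is no sign of inflation.

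**The case against.** **Choosing covariates by test might be thought to inflate the .05 level.** A reader might infer this, but step 6 does not support it. Nor is the unadjusted comparison biased: randomisation protects it whether or not the variable is in the model.

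**The variable has not been shown to be prognostic.** This stands. D.5.1 says only that it is a potential confound, and no association with outcome is reported. Any gain must come over and above the outcome's baseline score, which is already fixed and may overlap with prior treatment. Hence the range, with a gain that may be as small as 1 point of power.

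**The precision figures do not hold for the urine screen or recidivism.** This also stands. In logistic regression, adding a prognostic covariate raises the standard error of the log odds ratio and makes the effect a conditional one. In simulation at N = 416 with about 50% positive, and assumed covariate log odds ratios of 0.3, 0.5 and 0.8 per SD, the mean standard error went from .200, .200 and .199 to .202, .206 and .214. Power can still rise (from .62 to .67 at the strongest value), but the table in step 4 cannot be applied. The case for fixing the covariate in those models is prespecification.

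**The count of chance covariates is soft.** Agreed: the number of variables and their independence are assumed. D.7.1 applies Benjamini-Hochberg to the multiple comparisons without saying whether the balance tests are among them. If they are, the chance of any false flag drops to about 5%, but treatment use would then enter even less often.

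**D.3.2 speaks of all treatment outside the study, so follow-up treatment might seem to belong in the model.** The documents do not support that. The intervention (BMI) includes a treatment referral (D.4.4), so later treatment may be one of its effects, and D.5.1 keeps those data descriptive or exploratory.

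**The wide spread is stated for the SC condition.** True. That it applies to both arms is an inference, though a direct one, since the intervention arm also receives SC.

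**Conclusion.** The point holds as one of prespecification and modest lost efficiency. The clause on baseline differences is the only stated route by which non-study treatment can enter the ANCOVA, logistic or growth models; the SEM's separate list omits it. Under valid randomisation, and if the balance tests use .05, the rule excludes it about 95% of the time per tested variable. The SAP therefore does not reliably carry out what D.3.2 undertakes.

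The size depends wholly on an assumed prognostic strength: for 2% to 10% of extra variance, a 2% to 9% smaller standard error in the ANCOVA. It is not a finding of bias or of a weakened alpha. It is worth correcting because the correction is nearly free.

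**What to change.** In SAP D.7:

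1. Delete "as well as any other variables found to differ at baseline".
2. Add one fully defined baseline variable to the fixed covariates of the ANCOVA and logistic models. For example: any substance use treatment in the 6 months before Baseline B, yes/no, from the Economic Form-90. A session count would also serve, but the coding must be settled now; leaving it open would bring the choice back. The growth curves inherit the change.
3. Keep the baseline comparison as a descriptive table that does not alter any model.
4. State that only the pre-randomisation value is used. Adjusting for it removes none of the BMI's effect.
5. Decide whether it also enters the SEM. If so, restate the 94 degrees of freedom and the associated power in D.7.1.

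Cost: a short change of wording, no new data collection, one degree of freedom per ANCOVA or logistic model, and a restated SEM figure if the variable is added there.
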